8.2 Sample size estimate

We anticipate that identification of at least 700 individuals in the intervention group and control group should be sufficient to detect an average change of 0.5% in A1c, assuming an $\alpha=0.05$, $1-\beta=0.80$, A1c standard deviation=1.9, and a verbal informed consent rate of 45%, including clustering and non-differential loss-to-follow up between the study groups (Table 5). With this sample size, we should also have the ability to detect differences in the adherence outcomes (Table 6).

Based on feasibility information from Horizon, we anticipate that of the 315 patients in the intervention group who are likely to be reached by pharmacists (45%), at least 236 will have usable follow-up data. This proportion of reached patients has been observed in prior, pilot studies that have used a similar approach.²⁵ In order to observe an overall A1c difference of 0.5% in the study population, these contacted patients must have a underlying mean A1c change of ~0.49% (Figure 3). This difference is in line with what clinical guidelines consider to be a clinically meaningful difference in glycaemic control. This A1c difference has been observed in prior work with clinical pharmacists.⁸ This sample size would also provide enough patients for the predictive analytics work, given the relative non-rare nature of the study outcomes (glycemic control and medication adherence).

Table 5. Justification: A1c power calculation parameters and ranges

Range of parameters: input ranges	A1c difference: 0.5% Sample size (N range)/group
A1c SD: 1.9-->N1	228
Intra-cluster correlation (N ₂ =N ₁ * 1.03)	235
Loss-to-follow-up (LTF): 15-30%	(best case: 276, worst case: 335)

Date

(N ₃ =N ₂ /[1-rate])	
Pharmacist contact rate: 35-50% (N ₄ =N ₃ /rate)	(best case: 552, worst case: 959)
Total	45% reach rate and 25% LTF: 696 patients/arm

Power (1-β): 0.80; Alpha (α): 0.05

Explanation of study parameters – Primary outcome (A1c)

- 1) Standard deviation of A1c: ranges between 1.0 and 2.0, depending on study length and average baseline A1c values. The most commonly cited value is 1.9, assuming equal variances between the groups. This would be non-differential between study groups.
- 2) Intra-cluster correlation: Other studies have also incorporated intra-cluster correlation (ICC) within PCP clinics (~0.03 for small pilot studies). This would be non-differential between study groups.

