1.2 Study design

ENGAGE-DM (ENhancing outcomes through Goal Assessment and Generating Engagement in Diabetes Mellitus) is a pragmatic, prospective, intention-to-treat, randomized controlled trial designed to examine the impact of a novel intervention among patients with T2D that combines behavioral interviewing and shared decision-making delivered by pharmacists over the telephone compared with usual care. After the completion of the trial, we will examine whether a patient's response to the intervention could have been predicted based on their demographics, comorbidities or medication treatment-related factors.

This trial is being conducted among commercially-insured individuals whose medical and prescription benefits are administered by Horizon Blue Cross Blue Shield of New Jersey (Horizon). Horizon is the largest health insurer in New Jersey and administers plans for over 3.8 million beneficiaries.

Following the principles of pragmatic trial design, potentially eligible patients for inclusion in this study were those who: (1) were ≥ 18 years of age, (2) had filled a prescription for 1 or more oral hypoglycemic agents within the prior 12 months, and (3) had evidence of poor glycemic control (A1C $\geq 8\%$) within the previous 6 months, assessed using the most recent HbA1c lab values provided to Horizon Blue Cross Blue Shield. If patients had multiple HbA1c lab values, the latest value was evaluated. An HbA1c threshold of 8% was chosen based on the minimum threshold that nearly all patients should achieve based on guidelines from the American Diabetes Association (ADA); it is also a threshold for major quality measures for health plans. Patients were excluded if, prior to identification, they had fewer than 3 months of continuous enrolment in the health plan, had recently filled insulin (e.g., to exclude patients with type 1 diabetes), or had no available telephone contact information, which would preclude contact for enrolment and delivery of the intervention.

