1.3 Number of subjects

In total, 1,400 subjects were randomized in a 1:1 ratio to the intervention or control group. Our study was designed to be sufficiently powered to detect small but clinically meaningful changes in the primary outcome of HbA1c change.

We considered the following assumptions in the power calculations. Assuming that 30% of study subjects in the intervention arm agree to participate in the intervention, we randomized 700 individuals

to each of the intervention and control groups in order to achieve 80% power to detect an average change in HbA1c of 0.5% between the intervention and control groups at an alpha threshold of 0.05 with a HbA1c standard deviation=1.9 (the most commonly cited value in the literature for HbA1c), accounting for 25% rate of loss-to-follow-up.^{1,2} We used Proc Power in SAS 9.4 (Cary, NC) using a t-test and adjusted the sample size to account for the reach rate. Because patients may change insurance, in particular at the end of the calendar year, we accounted for a rate of non-differential loss-to-follow-up of 25% rate. There may also be patients who do not have follow-up HbA1cs, despite restricting to patients whose providers have at-risk contracts with Horizon Blue Cross Blue Shield. As described later in Section 3, we will use multiple imputation methods to account for patients with no follow-up HbA1c values. In addition, this proportion of patients who agree to participate in this intervention has been observed in prior studies that have used a similar approach.²⁵ Finally, the proposed difference of HbA1c of 0.5% is the level that clinical guidelines consider to be a clinically meaningful difference in glycemic control. This HbA1c difference has also been observed in prior work with clinical pharmacists.⁸ Because the primary outcome is HbA1c change, we expect to see clinically meaningful differences in these levels within the 11 to 12-month follow-up period.^{3,4}

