3. PRIMARY AND SECONDARY VARIABLES

3.1 Primary outcome (mean change in glycemetic control):

The primary outcome of interest will be the pre- to post-intervention change in mean HbA1c levels to the end of the 12-month follow-up period. Follow-up will begin from the date of treatment group assignment. The data for this outcome will be based on laboratory information that Horizon Blue Cross Blue Shield of New Jersey receives from over 200 patient-centered medical homes and other population health programs used for quality improvement monitoring. This laboratory information will be used to measure the change in HbA1c levels at the end of follow-up. In specific, the HbA1c result recorded closest to the 12-month end of follow-up as provided in the laboratory data will be used for the primary analysis.

For subjects with missing outcome data, multiple imputation will be used to impute missing follow-up values to calculate the change in HbA1c levels.¹⁰ Of note, all patients by definition for inclusion in the study will have baseline HbA1c values. This imputation approach is used to generate multiple results for missing values based on the underlying distribution of the available data. We will test the robustness of this approach with sensitivity analyses that use alternative methods of handling missing data, including complete case analysis.

This outcome will be analysed formally. We will also explore any potential differences in effectiveness by the pharmacist delivering the intervention.

3.2 Secondary outcome (proportion achieving glycemic control):

The secondary glycemic outcome will include the proportion of patients achieving optimal glycemic control. Optimal glycemic control will be defined as the proportion of patients who achieved an HbA1c result <8.0% in the 12-month follow-up period. This conservative threshold is based on the minimum threshold that nearly all patients should achieve based on guidelines from the American Diabetes Association (ADA) and quality measures used to assess the performance of health plans.^{11,12} In specific, we will use the laboratory information provided to Horizon and will use the HbA1c result recorded closest to the 12-month end of follow-up for the primary analysis.

For subjects with missing outcome data, we will use multiple imputation to impute missing follow-up values to calculate the proportion of patients who achieved this threshold.

This outcome will be analysed formally.

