4.2 Analysis methods

4.2.1 Primary objective (Effectiveness of intervention):

Baseline characteristics:

We will measure key baseline characteristics in the 12-months prior to randomization in the pharmacy and medical claims data and enrolment files. These characteristics will include sociodemographic characteristics, such as age and sex, which will be measured in the enrolment files. We will also measure baseline clinical characteristics such as the presence of coronary artery disease, chronic obstructive pulmonary disease, asthma, hypertension, hyperlipidemia, congestive heart failure, depression, liver disease, chronic kidney disease, osteoporosis and prior macrovascular complications. These will be measured in medical claims files using ICD-10 codes. We will also measure the type of oral glucose-lowering agent used in the baseline period (e.g., medical class), average PDC at baseline, and whether or not the medication is branded. We will also measure patients' latest copayments for oral glucose-lowering agents in the baseline period. Finally, we will also measure baseline healthcare resource utilization variables as characteristics including the number of days hospitalized and the number of physician office visits.

We will report, in tabular format, the means and frequencies of baseline characteristics prior to assignment separately for patients in the intervention and control groups and compare these values using t-tests, chi-square tests, and their non-parametric analogues, as appropriate. We will provide absolute standardized differences between the two treatment groups.

Primary analyses:

Primary outcome (change in HbA1c): In the primary analysis, the primary outcome, mean change in glycemic control, will be compared using generalized estimating equations with an identity link function (as a continuous variable) and normally distributed errors within the imputed full analysis set, as described above. Data will be presented as the unadjusted absolute difference in the change in HbA1c between the groups along with 95% confidence intervals.

Secondary outcome (proportion achieving glycemic control)

1) *Proportion of patients achieving optimal glycemic control* (defined by HbA1c < 8): This outcome will be compared using generalized estimating equations with a logit link and binary distributed errors. Data will be presented as the unadjusted odds ratio for optimal glycemic control between the groups along with 95% confidence intervals.

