Secondary outcomes (medication adherence):

1) *Mean PDC in each study arm:* This outcome will be compared using generalized estimating equations with an identity link function and normally distributed errors. Data will be presented as the unadjusted absolute difference between the groups along with 95% confidence intervals.

2) *Proportion of patients achieving optimal adherence* (defined by ≥ 0.80 PDC): This outcome will be compared using generalized estimating equations with a logit link and binary distributed errors. Data will be presented as the unadjusted odds ratio for optimal adherence between the groups along with 95% confidence intervals.

Secondary analyses:

Healthcare resource utilization and spending: Secondary analyses of healthcare resource utilization will use a similar approach as the primary analysis among the full analysis set, except that we will use log link functions with Poisson errors to describe the count data. Health spending will also be evaluated with variances proportional to the mean (e.g., Poisson-like errors) using log-link functions in generalized estimating equations, which has been found to describe insurer healthcare spending data accurately based on prior research.⁵ Data will be presented as the unadjusted odds ratio along with 95% confidence intervals.

Adjusted analyses: If there are differences in baseline characteristics between study groups that are believed to be confounders (defined by a standardized mean difference of >0.1), we will repeat all of our analyses for the primary and secondary outcomes after adjusting for these covariates in multivariable regression. We will present these as adjusted effect estimates along with 95% confidence intervals.

Interactions: We will also explore any potential differences in effectiveness by the specific pharmacist delivering the intervention by evaluating effect measure modification and using interaction terms within the main model for the primary outcome of change in HbA1c. We will present p-values for interactions.

Subgroups: Subgroup analyses of the primary outcome (change in HbA1c) will also be performed for key subgroups, according to age, sex, depression, and baseline medication adherence levels. These analyses will be performed separately among subgroups of the characteristics and compared between the treatment arms. Data will be presented as unadjusted absolute differences in the change in HbA1c along with 95% confidence intervals.

Sensitivity analyses:

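### The primary HbA1c comparison is an unadjusted change score although every patient has a baseline HbA1c; prespecifying baseline HbA1c as a covariate costs almost nothing and may narrow the interval.

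*SAP*

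**What the plan says.** SAP section 4.2.1 compares change in HbA1c by GEE with an identity link and "normally distributed errors within the imputed full analysis set, as described above". The reported quantity is fixed in the next sentence: "Data will be presented as the unadjusted absolute difference in the change in HbA1c between the groups along with 95% confidence intervals". No covariate is named.

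SAP section 3.1 states: "Of note, all patients by definition for inclusion in the study will have baseline HbA1c values". Missing follow-up values are multiply imputed, but the imputation variables are not listed. The only description is: "This imputation approach is used to generate multiple results for missing values based on the underlying distribution of the available data".

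Adjustment appears under the secondary analyses in SAP section 4.2.1, and is conditional: "If there are differences in baseline characteristics between study groups that are believed to be confounders (defined by a standardized mean difference of >0.1"). Protocol section 8.1 likewise ties multivariable adjustment to imbalance that has been observed. HbA1c is not named in the SAP's list of baseline characteristics. The sensitivity analyses (complete case and longitudinal GEE) do not name it as a covariate either.

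**The concern.** Baseline HbA1c is complete, already collected, and likely to be related to follow-up HbA1c. A change score uses it in one particular way: it subtracts the baseline with a coefficient of exactly 1. Patients enter because their latest HbA1c is at or above 8%, so some regression toward the mean, and hence a slope below 1, is a natural expectation, though it is an assumption here. When the slope is not 1, part of the baseline variation stays in the change score as noise.

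The imbalance rule does not fill the gap. It brings baseline HbA1c in only after an imbalance has been seen, and the adjusted result is then not the primary one. A covariate used for precision should be chosen in advance for its relation to the outcome, whatever imbalance happens to appear. At stake is the width of the primary confidence interval; the validity of the estimate is not in question.

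**Working it through.** **The planning figure.** Protocol section 8.2, Table 5, uses a difference of 0.5, SD 1.9, two-sided alpha 0.05 and 80% power. A t-test calculation gives 227.6, so 228 per arm. Then 228 × 1.03 = 234.8 (235), 235 / 0.75 = 313.3, and 313.3 / 0.45 = 696.3, against the stated 696. So 1.9 enters as the SD of whatever is compared. The protocol describes it only in general terms ("Standard deviation of A1c: ranges between 1.0 and 2.0, depending on study length and average baseline A1c values") and does not say whether it is the SD of a level or of a change. Neither document gives a correlation between baseline and follow-up.

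**Why adjustment cannot lose in large samples.** Let s0 and s1 be the baseline and follow-up SDs and r their correlation.

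- Variance of the change score: s0² + s1² − 2·r·s0·s1
- Variance after adjustment: V = s1²(1 − r²)
- Difference: A = (s0 − r·s1)², which is never negative

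A is zero only when s0 = r·s1, that is, when the slope of follow-up on baseline is 1. The identity link leaves the estimand, the difference in mean change, as it was. Allocation is equal ("In total, 1,400 subjects were randomized in a 1:1 ratio to the intervention or control group"), so the result also holds if the slope differs by arm. A simulation with 525 per arm (700 less 25%) gave adjusted-to-unadjusted variance ratios of 0.76 at slope 0.5, 1.00 at slope 1, and 0.77 with slopes of 0.3 and 0.7 in the two arms.

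**Share of variance removed.** In observed data s = A / (A + V). With k = s0/s1, s = (k − r)² / (k² + 1 − 2kr). In the imputed set, let a fraction f = 0.75 be observed, missing at random, with baseline in the imputation model. The unadjusted variance is then proportional to A/n + V/(f·n) and the adjusted variance to V/(f·n). The share removed is f·s / (f·s + 1 − s), and the interval narrows by 1 − √(1 − share).

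| Assumed scenario | Observed data | Imputed set | CI narrower by |
|---|---|---|---|
| Normal HbA1c cut at 8% (latent mean 7–8, SD 1.5–1.9, r 0.4–0.8) | 2.6–13.5% | 2.0–10.5% | 1–5% |
| k = 0.6, r = 0.3 / 0.5 / 0.6 | 9 / 1 / 0% | 7 / 1 / 0% | 4 / 0.5 / 0% |
| k = 0.8, r = 0.4 / 0.6 / 0.8 | 16 / 6 / 0% | 12.5 / 4.5 / 0% | 6 / 2 / 0% |
| k = 1, r = 0.7 / 0.5 / 0.2 | 15 / 25 / 40% | 12 / 20 / 33% | 6 / 11 / 18% |

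In the first row, r is the correlation before the cut. At its upper end (mean 8, SD 1.9, r 0.4), the baseline variance after the cut is 3.61 × (1 − 0.798²) = 1.312. Then A = 0.6² × 1.312 = 0.472, V = 3.61 × 0.84 = 3.032, and s = 0.472 / 3.505 = 13.5%. In the imputed set this is 0.101 / 0.966 = 10.5%.

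The first row is the one tied to a feature of this trial: SAP section 1.2 sets entry at 8% ("An HbA1c threshold of 8% was chosen based on the minimum threshold that nearly all patients should achieve"). The cut narrows the baseline distribution, so the equal-SD row is probably the upper end.

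**Simulation of the imputed analysis** (700 per arm, 25% missing at random, imputation on arm and baseline, 20 imputations, Rubin's rules, 2,500 replicates). The variance saved was 11.9 / 20.6 / 32.7% for the equal-SD row (closed form 11.7 / 20.0 / 33.3%), 10.6% at the upper end of the first row (10.5%) and 1.7% at its lower end (2.0%). Both estimators were unbiased.

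**Cost if the slope is exactly 1.** 1 / (2 × 700 − 4) = 0.07% of variance.

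**How often the imbalance rule would act.** With 700 per arm the standard error of a standardized mean difference is √(2/700) = 0.053. Chance alone takes it beyond ±0.1 about 6% of the time.

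**The case against.** The strongest reply is that nothing here is wrong. The change score is valid, its analysis set and sensitivity analyses are stated, and the choice lies between two sound estimators. That stands, which is why this is a recommendation and not an error.

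The second reply is that the benefit is small and assumed. This stands in part: every percentage rests on assumed inputs. If 1.9 is taken as the SD of change with 525 per arm, power for 0.5 is already 98.9%, and removing 2.0 to 10.5% of the variance takes it only to 99.1–99.5%. If the intention-to-treat effect is diluted to 0.45 × 0.5 = 0.225 (an assumption), power moves from 48% to 49–53%.

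Third, a change score already subtracts the baseline, so only (1 − slope) times any chance imbalance remains. That is correct. Under the cut-at-8% scenarios this remainder has a standard error of about 0.008 to 0.037 HbA1c points. It is the term A above, so removing chance imbalance is the same gain and not a second one.

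Fourth, the no-loss result is a complete-data argument. The imputed-set figures also need missingness at random, arm and baseline HbA1c in the imputation model, and independent patients, whereas protocol section 8.2 allows for clustering by clinic. These are fair limits on the size of the gain. None of them favors fixing the slope at 1.

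**Conclusion.** The concern holds. The primary estimate leaves out a complete baseline measure that could be used at almost no cost, and the conditional rule would rarely bring it in. The issue is precision and prespecification; bias does not arise. The most relevant assumed scenario, truncation at 8%, gives an interval about 1 to 5% narrower. The gain is larger if the baseline and follow-up SDs are closer to equal and close to nil if the slope is near 1. No single figure follows from the documents. The change is worth making because the downside is about 0.07% of variance. Confidence in the direction is high; confidence in the size is limited.

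**What to change.** In SAP section 4.2.1, before outcome data are released:

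- Name continuous baseline HbA1c as a covariate in the primary identity-link GEE, and make the adjusted difference in change with its 95% CI the primary result.
- Keep the unadjusted difference in change as a supportive result.
- In SAP section 3.1, list the imputation variables, including at least arm and baseline HbA1c, so that the imputation model matches the analysis model.
- Keep the analyses triggered by a standardized mean difference above 0.1 as supplementary.
- Record the change in SAP section 6, now marked not applicable, because protocol section 8.1 provides for adjustment only where imbalance is observed.

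The cost is SAP wording; no new data are needed. SAP section 2.2 says the full data reach the investigators only after the late March 2018 lockout, so the choice can be fixed credibly before then.

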For each outcome (e.g., $HbA1c < 8\%$ and $PDC \geq 0.80$), we will first estimate a model that includes only demographic and clinical characteristics. We will then estimate additional models that include these predictors as well as baseline medication adherence information and initial screening characteristics (e.g., Morisky score, PHQ-2 score, CHAI score). In addition, as initial filling information have been shown in previous work to be highly predictive of subsequent medication adherence, we will also include initial post-baseline filling information to assess the ability to predict medication adherence and glycemic control in the subsequent follow-up period.³⁵ Receipt of the pharmacist intervention will be tested using an interaction term so the logistic regression will provide estimates on all patients and not just those receiving the intervention. We will also repeat the analyses among the subgroup of intervention patients who had at least 1 telephonic encounter with a pharmacist to examine which set of characteristics are most predictive of the response to the intervention. Model estimation will be repeated among relevant patient subgroups (e.g., gender, age) to see if there are any differences in predictive ability.

Models among each of the control and intervention groups will be predicted using both logistic regression and generalized boosting regression, a data mining technique that generates a prediction model through building many regression trees with the potential for many interactions among the predictors.³⁷ Through these many regression trees, the model can incorporate a number of non-linear associations between the predictors and the outcomes; this approach is considered to be one of the best prediction approaches. Alternative methods of clustering patients who are most likely to respond will also be explored, including machine learning to develop models algorithmically, to partition patients into clusters that have a similar likelihood of experiencing the clinical outcomes.³⁸

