3.3 Secondary outcome (two medication adherence outcomes):

Medication adherence will be measured using filling patterns in pharmacy claims data for medications that qualified a patient for inclusion in the study.¹³ For each medication, we will create a drug supply diary linking all observed fills after initiation based on dispensing date and days' supply. Different drugs in the same chemically-related therapeutic class (e.g., sulfonylureas) will be considered to be interchangeable. We will allow for up to 180 days of carryover supply. From these supply diaries, we will calculate the proportion of days that patients had medications available to them, or the proportion of days covered (PDC), by dividing the number of days with medication available by the number of days during follow-up.¹⁴ If a patient loses continuous eligibility during the year after the index date, the PDC will be calculated based on the number of days available. If a patient loses continuous eligibility during the year after the index date, they will be censored on that date, and the PDC will be calculated based on the number of days available. In this PDC measurement, if patients had at least one antidiabetic medication available, then they will be considered to be adherent for that day. This definition allows for outcome measurement even when patients switch (e.g., switch from metformin to a sulfonylurea) or intensify therapy (e.g., adding a second oral diabetes medication or injectable medication).

Using this PDC measure, we will observe *1) the mean PDC in each study arm* and *2) the proportion of patients achieving optimal adherence* (defined by ≥ 0.80 PDC) as adherence outcomes in the follow-up period. In a sensitivity analysis of this outcome, medication adherence will be measured by calculating the PDC beginning from the first fill of a medication after assignment until the end of the 12-month follow-up. There will be no missing data for these outcomes, as previously described.

These outcomes will be analysed formally.

3.4 Secondary analyses:

Resource utilization:

As secondary analyses, we will also measure healthcare spending and healthcare resource utilization, including outpatient visits, emergency room visits, and hospitalizations, in the follow-up period in the medical and pharmacy claims data. Healthcare spending will be measured as total allowed amounts in

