4. ANALYSIS METHODS

4.1 General principles

The primary objective is to examine whether a two-stage process of shared decision-making and behavioral interviewing improves glycosylated hemoglobin (HbA1c) control and medication adherence among patients who have poorly-controlled diabetes. This is a superiority trial.

The primary outcome is pre to post change in mean HbA1c level from baseline to the follow-up period. There is only one primary outcome, so there will be no multiple testing adjustments.

The primary and secondary outcomes will be evaluated using intention-to-treat principles among all assigned patients. Within the intervention group, patients who choose to speak with a pharmacist may differ from those who do not, and an intention-to-treat analysis in this randomized study ensures unbiased comparisons to the control group.

For all outcomes, statistical significance is defined based on $p < 0.05$ level and using two-sided steps. For continuous data, we will present the results as n and mean (standard deviation). For binary data, we will present the data as n (%). We further describe the analysis of and tests used for each of the outcomes in Section 4.2.

The secondary objective is to develop prediction models and examine their ability to predict response to the study intervention based on baseline patient characteristics, such as sociodemographic, clinical, and medication use characteristics, as well as initial receptiveness to changing health behaviors. We will describe the analysis of this objective further in Section 4.2.

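### The two formal secondary adherence outcomes are analysed without baseline PDC, which the SAP already measures, so precision that is available at almost no cost is left unused

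*SAP*

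**What the plan says.** SAP 3.3 defines two adherence outcomes, mean PDC and the proportion with PDC of at least 0.80, and says of them: "These outcomes will be analysed formally". Both are follow-up levels, not changes from baseline.

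SAP 4.2.1 compares each by generalised estimating equations and names no baseline covariate. For mean PDC: "Data will be presented as the unadjusted absolute difference between the groups along with 95% confidence intervals". For the threshold outcome: "Data will be presented as the unadjusted odds ratio for optimal adherence between the groups along with 95% confidence intervals".

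The baseline list in SAP 4.2.1, taken from the 12 months before randomisation, includes "average PDC at baseline, and whether or not the medication is branded". Eligibility (SAP 1.2) requires that a patient "had filled a prescription for 1 or more oral hypoglycemic agents within the prior 12 months", so every patient has some pre-assignment fill history. Only three months of continuous enrolment are required, so some histories are short.

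The one route to covariate adjustment is a repeat of the primary and secondary analyses for baseline differences regarded as confounders, "defined by a standardized mean difference of >0.1". Protocol 8.1 likewise adjusts only for observed imbalance. In SAP 4.2.2, by contrast, baseline medication adherence is added to the models that predict PDC of at least 0.80.

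**The concern.** In a randomised comparison, a baseline covariate earns its place in the model by predicting the outcome, not by differing between arms. A patient's earlier PDC is a natural predictor of later PDC, and the SAP treats it as a candidate predictor in Aim 2. The HbA1c outcome at least uses its baseline value by taking a change; the PDC outcomes make no use of theirs.

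The planned trigger depends on chance imbalance, so in most realisations baseline PDC would never enter an adherence model. When it did, this would only be in a repeat beside the unadjusted result.

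What is at stake is interval width and power. The differences of interest are small (5 points in Protocol Table 6, 4 points in SAP 1.3). Under intention to treat they are also diluted by partial uptake, planned at 45% in the Protocol and 30% in the SAP.

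**Working it through.** **Inputs from the documents.** 700 per arm; two-sided alpha 0.05; power 0.80; N1 = 253 for a 5-point difference (Protocol Table 6); imbalance trigger 0.1; no substantial loss to follow-up expected for adherence (SAP 1.3).

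**Inputs not in the documents.** The SD of PDC and the correlation r between baseline and follow-up PDC. Ranges are shown for both.

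**The plan's own figures.**
- Table 6, later steps: 253 × 1.03 = 261; 261 / 0.85 / 0.45 = 682. This reproduces.
- Table 6, N1: as proportions, 0.50 against 0.55 needs 1,565 per arm, not 253. As means, SD = 5 / (1.960 + 0.842) × sqrt(253/2) = 20.1 points. The figure therefore implies an unstated SD of about 20.
- SAP 1.3, 4 points: the chi-square test named there, for 0.50 against 0.54, needs 2,448 per arm and has 32% power at 700. As means, 4 points at 80% power with 700 per arm corresponds to an SD of 26.7. The figure does not reproduce as described. That is a separate matter, and nothing below depends on it.

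These results suggest an SD range of 20 to 30 points.

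**How often the trigger would fire.** The standardised difference of one covariate has standard error sqrt(2/700) = 0.0535. Then z = 0.1/0.0535 = 1.87, and P(|SMD| > 0.1) = 2 × (1 − Φ(1.87)) = 0.061, about 6%.

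**Mean PDC.** Adjusting for baseline PDC multiplies the variance of the difference by 1 − r², whatever the SD.
- Equivalent unadjusted sample size = 700 / (1 − r²).
- Detectable difference = 2.802 × SD × sqrt((2/700) × (1 − r²)).
- 95% CI half-width = 1.96 × SD × sqrt((2/700) × (1 − r²)).

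| r | Variance reduction | Equivalent n per arm | Half-width, SD 20 | Detectable, SD 20 | Detectable, SD 30 |
|---|---|---|---|---|---|
| 0 (as planned) | 0% | 700 | 2.10 | 3.0 | 4.5 |
| 0.3 | 9% | 769 | 2.00 | 2.9 | 4.3 |
| 0.5 | 25% | 933 | 1.81 | 2.6 | 3.9 |
| 0.7 | 49% | 1,373 | 1.50 | 2.1 | 3.2 |

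An illustration with dilution: if a 5-point effect occurs only in the 45% reached, the intention-to-treat difference is 5 × 0.45 = 2.25 points. At SD 20, power rises from 56% to 60%, 68% and 84% for r = 0.3, 0.5 and 0.7. At SD 30 it rises from 29% to 31%, 37% and 50%.

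**PDC of at least 0.80.** There is no equally simple formula, so this was simulated: 1,500 trials of 700 per arm, a normal latent PDC with correlation r to baseline, a latent shift of 0.15 SD, and 30% or 50% of controls above the threshold. The adjusted logistic model was standardised over the sample to a marginal odds ratio.

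| r | Variance ratio, 30% above | Variance ratio, 50% above | Reduction |
|---|---|---|---|
| 0.3 | 0.947 | 0.949 | about 5% |
| 0.5 | 0.829 | 0.832 | about 17% |
| 0.7 | 0.695 | 0.655 | 30-35% |

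Without standardisation, the conditional log odds ratio is a different estimand and its standard error rises. At 50% above threshold and r = 0.5 it goes from 0.107 to 0.117, although power still rises from 60% to about 70%. A narrower interval on the effect the SAP reports therefore needs the standardisation step.

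**The case against.** An unadjusted main analysis with a prespecified adjusted repeat is a legitimate choice in a pragmatic trial. It is unbiased, and its interval already allows for chance imbalance. No document gives r. At r = 0.3 the detectable difference moves only from 3.0 to 2.9 points. Short enrolment or a recent treatment start could lower r, because a patient who has just begun therapy would show low coverage over a full look-back without being non-adherent. All of this stands: it limits how firmly the size of the gain can be stated and makes the definition of baseline PDC part of the fix. It does not remove the gain, because any nonzero r reduces the large-sample variance and the covariate is already planned.

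Three stronger readings are tempting and are not supported.
- A reader might cite Protocol 8.1 on initial filling as proof that baseline PDC is strongly prognostic. That sentence concerns fills after baseline. SAP 4.2.2 is the relevant text, and it lists baseline adherence as a predictor without claiming any strength.
- A reader might say that half of the primary objective is compromised, since it asks whether the intervention "improves glycosylated hemoglobin (HbA1c) control and medication adherence among patients who have poorly-controlled diabetes". SAP 4.1 states that there is a single primary outcome, HbA1c change; both PDC measures are secondary.
- A reader might extend the point to healthcare utilisation. For hospitalisation, the planned baseline variable is days in hospital while the outcome is the number of admissions, so no matching baseline count is specified. No gain has been calculated for any utilisation outcome.

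**Conclusion.** The point holds as one of efficiency. Both formal secondary adherence outcomes omit a baseline measurement that the SAP already collects, and the imbalance rule would bring it in by chance in only about 6% of trials.

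For mean PDC the variance reduction is 9% to 49% over r = 0.3 to 0.7. For PDC of at least 0.80 it is about 5% to 30-35%, after standardisation. The percentages for mean PDC depend only on r; the detectable differences in points also rest on an assumed SD of 20 to 30. The figures assume all 700 per arm are analysed and leave out clustering.

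A reader might infer that chance imbalance in prior adherence biases the planned result. Under randomisation it does not. Confidence is high that precision is forgone and moderate about how much. This is a free improvement rather than an error in the plan.

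**What to change.** Amend SAP 4.2.1 before the outcome data are received; SAP 2.2 places the transfer of the full data after the database lockout in late March 2018.

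- **Mean PDC:** main model with arm and continuous baseline PDC, reporting the adjusted absolute difference and 95% confidence interval.
- **PDC of at least 0.80:** logistic model with arm and continuous baseline PDC, standardised over all analysed patients to a marginal odds ratio and a risk difference. Name the marginal effect as the estimand and state how its interval is obtained.
- **Baseline PDC:** compute it by the follow-up day rule over the available days before assignment, with one fixed rule for patients with short enrolment or a recent treatment start. A rule that uses only pre-assignment data keeps the comparison valid.
- **Sensitivity:** keep the unadjusted difference and odds ratio.
- **SAP section 6:** record the change from the Protocol.

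The cost is SAP wording and a modest amount of programming for the baseline rule and the standardisation. No new data are needed, and no loss of precision is expected at this sample size.
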